2. LIST OF ABBREVIATIONS

ACR	Albumin-to-Creatinine Ratio
ADA	American Diabetes Association
AE	Adverse Event
ADR	Adverse Drug Reaction
ANOVA	Analysis of Variance
BMI	Body Mass Index
CA	Competent Authority
CDS	Chinese Diabetes Society
CKD	Chronic Kidney Disease
CKD-EPI	CKD Epidemiology Collaboration
CI	Confidence Interval
CRA	Clinical Research Associate
CRF	Case Report Form
DPP-4	Dipeptidyl Peptidase-4
eCRF	Electronic Case Report Form
EDC	Electronic Data Capture
eGFR	Estimated Glomerular Filtration Rate
FAS	Full Analysis Set
FDA	Food and Drug Administration
FPG	Fasting Plasma Glucose
GCP	Good Clinical Practice
GLP-1	Glucagon Like Peptide-1
GPP	Good Pharmacoepidemiology Practices
HbA _{1c}	Glycated Haemoglobin A1c
HDL-C	High Density Lipoprotein Cholesterol
ICH	International Conference on Harmonisation
IEC	Independent Ethics Committee
IRB	Institutional Review Board
ISF	Investigator Site File
MAH	Marketing Authorisation Holder
OAD	Oral Antidiabetic Drug
PPG	Postprandial Plasma Glucose
LDL-C	Low Density Lipoprotein Cholesterol
SADR	Serious Adverse Drug Reaction
SAE	Serious Adverse Event
SEAP	Statistical and Epidemiological Analysis Plan
SCr	Serum Creatinine
SOP	Standard Operating Procedures
SUSAR	Suspected Unexpected Serious Adverse Reaction
T2DM	Type 2 Diabetes Mellitus
TC	Total Cholesterol
TCM	Trial Clinical Monitor
TG	Triglyceride
UA	Uric Acid
UAE	Urinary Albumin Excretion

4. ABSTRACT

Name of company: Boehringer Ingelheim			
Name of finished medicinal product: Not applicable			
Name of active ingredient: Not applicable			
Protocol date: 29 Sep 2016	Study number: 1218.174	Version/Revision: 2.0	Version/Revision date: 20 Dec 2016
Title of study:	Clinical characteristics, anti-hyperglycaemic treatment pattern and target attainment of type 2 diabetes mellitus patients in older population with or without albuminuria in China: A nationwide cross-sectional study		
Rationale and background:	China has the largest number of people with diabetes in the world, with the majority of the patient population over 60 years old and living in urban areas. However no data are available specifically on the clinical characteristics of the older population with type 2 diabetes mellitus (T2DM) in China		
Research question and objectives:	To investigate the level of glucose control, current anti-hyperglycaemic and the anti-hypertension/Lipid Lowering/anti-platelet treatment patterns, occurrence of the hypoglycaemia, and other potential factors associated with the level of glucose control in older population of T2DM in China		
Study design:	This is a multi-centre, cross-sectional, non-interventional study		
Population:	Outpatients with T2DM aged 60 years or older in China		
Variables:	
Primary outcome
 
 Proportion of patients attaining blood glucose control target defined as $HbA_{1c} < 7\%$ 
Secondary outcomes
 
 Renal function level of patients Treatment regimens for T2DM that patient are currently taking Proportion of macro-vascular and micro-vascular diabetic complications Proportion of Hypoglycaemic occurrence Proportion of Hypoglycaemia leading to therapy change Proportion of Anti-hypertension therapy usage Proportion of Lipid Lowering therapy usage Proportion of Anti-Platelet therapy usage Treatment adherence to Chinese T2DM guideline 2013 		
Data sources:	Examination report, outpatient medical Chart or other original medical record		
Study size:	1500 patients		

Proprietary confidential information © 2016 Boehringer Ingelheim International GmbH or one or more of its affiliated companies

Name of company: Boehringer Ingelheim			
Name of finished medicinal product: Not applicable			
Name of active ingredient: Not applicable			
Protocol date: 29 Sep 2016	Study number: 1218.174	Version/Revision: 2.0	Version/Revision date: 20 Dec 2016
Data analysis:	Descriptive statistics will be used to summarize the data in the study. The proportion of patients attaining HbA _{1c} <7% will further be tabulated by subgroups of demographic and clinical characteristics. A logistic regression model will be conducted to identify associations between overall blood glucose control and demographic and clinical characteristics.		
Milestones:	Start of data collection: 28 Feb 2017 End of data collection: 04 Sep 2017 Final report of study results: 31 Dec 2017		

5. AMENDMENTS AND UPDATES

Number	Date	Section of study protocol	Amendment or update	Reason
<1>	29 Nov2016	Front Page	Research question and objectives: To investigate the level of glucose control, current anti-hyperglycaemic and the anti-hypertension/Lipid Lowering/anti-platelet treatment patterns, occurrence of the hypoglycaemia, and other potential factors associated with the level of glucose control in older population of T2DM in China.	According to the conclusion of the investigator meeting. The Secondary Objectives have been amended.
<2>	29 Nov2016	4	Research question and objectives: To investigate the level of glucose control, current anti-hyperglycaemic and the anti-hypertension/Lipid Lowering/anti-platelet treatment patterns, occurrence of the hypoglycaemia, and other potential factors associated with the level of glucose control in older population of T2DM in China.	According to the conclusion of the investigator meeting. The Secondary Objectives have been amended.
<3>	29Nov2016	4	add 6 secondary outcomes 
 • Proportion of Hypoglycaemic occurrence • Proportion of Hypoglycaemia leading to therapy change. • Proportion of Anti-hypertension therapy. • Proportion of Lipid Lowering therapy. • Proportion of Anti-Platelet therapy. • Treatment adherence to Chinese T2DM guideline 2013. 	The Secondary Objectives have been amended. Variable has been changed accordingly.

<4>	29Nov2016	4	
Milestones: Start of data collection: 28 Feb 2017 End of data collection: 04 Sep 2017 Final report of study results: 31 Dec 2017
	
According to the protocol amendment, the milestone has been changed.

<5>	29Nov2016	6	
Milestones: Start of data collection: 28 Feb 2017 End of data collection: 04 Sep 2017 Final report of study results: 31 Dec 2017
	
According to the protocol amendment, the milestone has been changed.

<6>	29Nov2016	8	
The secondary objectives are:
 
 • to investigate the anti-hyperglycaemic treatment patterns of the study population. • to investigate occurrence of the hypoglycaemia and hypoglycaemia leading to therapy change. • to investigate the anti-hypertension/Lipid Lowering/anti-platelet treatment patterns of the study population. • to investigate the clinical characteristics of the study population. • to investigate clinical characteristics, anti-hyperglycaemic treatment pattern and blood glucose control in older T2DM patients with albuminuria. • to investigate treatment adherence to Chinese T2DM guideline 2013 	
According to the conclusion of the investigator meeting. The Secondary Objectives have been amended.

<7>	29Nov2016	9.2.1	
Figure 1 – Study Flow of the cross-sectional study: Blood test:HbA_{1c}, FPG, LDL-C, HDL-C, TC, TG, Scr, UA; Urine test: Albuminuria, Urine WBC
	
As the Second Objectives have been changed, the visit schedules have been changed accordingly.

<8>	29Nov2016	9.2.1	
Inclusion Criteria #2: Outpatient with confirmed T2DM (According to Definition and Diagnosis Diabetes Mellitus :World Health Organization 1999 [R04-1142].)
	
The diagnosis criteria changed according to the decision of investigator meeting.

<9>	29Nov2016	9.2.2	
Amend following information under Collect the following information
 
 ○ Personal health history 
 ▪ Diabetes Mellitus history ▪ Chronic Kidney Disease history ▪ Anti-Hypertension therapy history ▪ Lipid Lowering therapy history ▪ Anti-Platelet therapy history ▪ hypoglycaemic history ○ Family health history (e.g., diabetes, hypertension, and Chronic kidney diseases) ○ Laboratory tests 
 ▪ HbA_{1c} ▪ Albuminuria ▪ Urine WBC ▪ Fasting plasma glucose (FPG), (examined within one month prior to the visit) ▪ Serum creatinine (SCr), uric acid (UA), high density lipoprotein cholesterol (HDL-C), low density lipoprotein cholesterol (LDL-C), triglyceride (TG), total cholesterol (TC) (If examined within three months prior to the visit, record the result; if examined without three months prior to visit, record the date of last examination and re-examine by investigator's judgment.) 	
As the Second Objectives have been changed, the visit schedules have been changed accordingly

<10>	29Nov2016	9.3.2	
Add following secondary outcomes
 
 • Proportion of Hypoglycaemic occurrence • Proportion of Hypoglycaemia leading to therapy change. • Proportion of Anti-hypertension therapy. • Proportion of Lipid Lowering therapy. • Proportion of Anti-Platelet therapy. • Treatment adherence to Chinese T2DM guideline 2013 	As the Second Objectives have been changed, some secondary outcomes have been added accordingly.
<11>	29Nov2016	9.3.3	PPG has been deleted.	As the Second Objectives have been changed, the visit schedules have been changed accordingly.
<12>	29Nov2016	9.7.1	The definition of FAS-Albuminuria has been updated, which takes urinary tract infection into account.	Based on investigators' consideration for determining micro-albuminuria diagnosis.
<13>	29Nov2016	9.7.3	The analyses for additional secondary endpoints have been added.	As the secondary endpoints have been updated, the corresponding analyses have been added.
<14>	29Nov2016	13	R04-1142 Definition, diagnosis and classification of diabetes mellitus and its complications: report of a WHO consultation. Part 1: diagnosis and classification of diabetes mellitus. WHO/NCD/NCS/99.2. Geneva: World Health Organization, Department of Noncommunicable Disease Surveillance, , 1 - 59 (1999)	Diabetes diagnosis criteria Changed as the investigator meeting decision. So the reference document changed.

6. MILESTONES

Milestone	Planned Date
Start of data collection	28 Feb 2017
End of data collection	04 Sep 2017
Final report of study results:	31 Dec 2017

7. RATIONALE AND BACKGROUND

Type 2 diabetes mellitus (T2DM) is a progressive disease caused by insulin resistance and decreased pancreatic β -cell function. The management of diabetes is very important in preventing diabetes complications, as well as long-term health problems. Despite a wide range of available therapies, the epidemic continues. Worldwide, the International Diabetes Federation estimates the global prevalence of diabetes in the older population (60–79 years) to be 18.6%—more than 134.6 million people—accounting for over 35% of all cases of diabetes in adults [[R14-1806](#)]. In 2013, China reported the highest number of people with diabetes in the world at 113.9 million and a prevalence of 11.6%, with a majority of the diabetes population over the age of 60 years and living in urban areas [[R13-5351](#)]. The high prevalence of diabetes is a public health issue as it increases the risk of other age-related diseases [[R16-4557](#)].

Diabetes in older adults is multifaceted in aetiology, caused by a combination of genetic and environmental factors. The risk factors include family history, age, lifestyle, illnesses and medications, as well as age-related decline in body functions [[P16-10791](#)]. The clinical profile of older patients with T2DM and their response to glycaemic control regimens are often different from that in younger patients [[P13-17218](#)]. Older patients with T2DM are at greater risk of hypoglycaemia [[R16-4558](#)] and other complications such as stroke and diabetic nephropathy [[R16-4559](#)]. Albumin is an abundant serum protein, which is undetectable in urine under normal health conditions. Therefore, increased urinary albumin excretion is an early clinical manifestation of diabetic nephropathy. Albuminuria is also associated with cardiovascular disease in patients with or without diabetes. Moreover, (micro-) albuminuria is often present at diagnosis in patients with T2DM and may reflect both underlying cardiovascular disease and diabetic nephropathy. Albuminuria is hence an established biomarker that identifies patients with T2DM at increased risk for vascular complications. It is reported that 26.1% of T2DM patients in Shanghai have albuminuria [[R16-4560](#)]. Therefore, T2DM management in older patients should be driven by strategies for effective and safe treatment aiming to reduce risk of chronic vascular complications of T2DM, as well as for improving or maintaining functional status and quality of life. The high burden of T2DM treatment in older patients and the associated adverse outcomes result in high health-care costs to both public and private payers.

Due to the lack of a large-scale, nationwide and systematically conducted survey, there are very limited data available on the characteristics and treatment patterns of older patients with T2DM in China. Furthermore, no data are available from patients with both T2DM and albuminuria in China. This makes it difficult for clinicians to effectively make medical decisions for patients with a variety of risk factors and complications, for healthcare professionals to assess the unmet medical needs and for healthcare organizations to assess the quality of patient care.

This study will help to better understand the current anti-hyperglycaemic treatment patterns, level of glucose control and unmet medical needs in older population of T2DM patients with or without albuminuria in China. In addition, it may improve the public awareness on anti-hyperglycaemic treatment, and provide evidence and direction for improving clinical practice.

8. RESEARCH QUESTION AND OBJECTIVES

The present study is to be conducted in older (≥ 60 years old) outpatients with T2DM in hospitals of China.

The primary objective is:

- to assess the level of blood glucose, measured by the proportion of patients attaining the blood glucose control target defined as $HbA_{1c} < 7\%$.

The secondary objectives are:

- to investigate the anti-hyperglycaemic treatment patterns of the study population.
- to investigate occurrence of the hypoglycaemia and hypoglycaemia leading to therapy change.
- to investigate the anti-hypertension/Lipid Lowering/anti-platelet treatment patterns of the study population.
- to investigate treatment adherence (follow up duration) to Chinese T2DM guideline 2013
- to investigate the clinical characteristics of the study population.
- to investigate clinical characteristics, anti-hyperglycaemic treatment pattern and blood glucose control in older T2DM patients with albuminuria.

9. RESEARCH METHODS

9.1 STUDY DESIGN

[figure not shown]
This is a multi-centre, cross-sectional, non-interventional study assessing blood glucose target attainment, anti-hyperglycaemic treatment pattern and the clinical characteristics in older outpatients with T2DM in hospitals of China. This study is designed to collect information of older T2DM patients in a real life setting. The primary outcome of this study is the proportion of patients attaining blood glucose control target defined as $HbA_{1c} < 7\%$. Demographic, clinical characteristics and treatment patterns of the study population will also be investigated. The primary method to be used is descriptive analysis.

9.2 SETTING

9.2.1 Study population

In this cross-sectional study, approximately 1500 patients will be recruited. Older outpatients with T2DM will be selected consecutively from departments of endocrinology in at least 30 hospitals of China.

Figure 1 – Study Flow of the cross-sectional study

Inclusion criteria

- Patient should fully know and understand the content of consent form, and the patient is willing and able to sign an informed consent form
- Outpatient with confirmed T2DM (According to Definition and Diagnosis Diabetes Mellitus :World Health Organization 1999[R04-1142])
- Age ≥ 60 years

Exclusion criteria

- Patients with type 1 diabetes mellitus or secondary DM
- Patients who are participating in any other clinical study, including any questionnaire-based study, any interventional study (including diet/counselling

based intervention), or any clinical study in which any medications (including Chinese herbal medications) are administered

9.2.2 Visit schedule

Patients will be recruited into the study in the order of their clinical visits scheduled. First 7 consented and suitable patients will be recruited for each site on each day, or fewer if without enough patients. One study visit is planned for each patient. Clinical assessments will be performed as part of routine clinical practice. Some laboratory tests results prior to the study can be used as source data as specified below. All data required should be entered into the Electronic Data Capture (EDC) System only after each patient has consented to participation.

During the study visit, the following procedures will be performed:

- Signature of informed consent and recording of the date informed consent was given
- Determination of eligibility by checking the inclusion/exclusion criteria
- Collect the following information
 - Demographic information
 - Personal health history
 - Diabetes Mellitus history
 - Chronic Kidney Disease history
 - Anti-Hypertension therapy history
 - Lipid Lowering therapy history
 - Anti-Platelet therapy history
 - hypoglycaemic history
 - Family health history (e.g., diabetes, hypertension, and Chronic kidney diseases)
 - Lifestyle
 - Physical examination
 - body weight
 - height
 - waist circumference
 - Vital sign
 - blood pressure
 - heart rate
 - Laboratory tests
 - HbA_{1c}
 - Albuminuria
 - Urine WBC
 - Fasting plasma glucose (FPG), (examined within one month prior to the visit)
 - Serum creatinine (SCr), uric acid (UA), high density lipoprotein cholesterol (HDL-C), low density lipoprotein cholesterol (LDL-C), triglyceride (TG), total cholesterol (TC) (If examined within three months prior to the visit, record the result; if examined without three

months prior to visit, record the date of last examination and re-examine by investigator's judgment.)

All of the laboratory tests will be performed by local laboratory and will be required on the same day of visit. The laboratory tests performed prior to the visit which can be used as source data are specified above.

Albuminuria can be measured in a random spot urine sample, a 24-h urine sample, or a timed urine sample. The results of albuminuria measurement will be categorized as normal, micro- and macro-albuminuria based on the definition in [Table 1](#).

Table 1 Definition of Albuminuria

Urinary albumin excretion	Random spot urine	24-h urine	timed urine
	ACR (mg/g)	24h UAE (mg/24h)	UAE (µg/min)
Normal	<30	<30	<20
Micro-albuminuria	30-300	30-300	20-200
Macro-albuminuria	>300	>300	>200

ACR: albumin-to-creatinine ratio; UAE: urinary albumin excretion

A log of all patients included in the study (i.e. having given informed consent) will be maintained in the Investigator Site File (ISF) at the investigational site.

Boehringer Ingelheim reserves the right to discontinue the study overall or at a particular study site at any time for the following reasons:

1. Failure to meet expected enrolment goals overall or at a particular study site.
2. Emergence of any efficacy/safety information that could significantly affect continuation of the study, or any other administrative reasons.
3. Violation of Good Clinical Practice (GCP), the study protocol, or the contract by a study site or investigator, disturbing the appropriate conduct of the study.

The investigator / the study site will be reimbursed for reasonable expenses incurred in case of study termination (except in case of the third reason).

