9.5 STUDY SIZE

According to a recent study, the proportion of patients with diabetes in China who achieved a target blood glucose level of HbA_{1c} <7% was 39.8% in patients aged 60-69 years old and 38.9% in patients aged 70 years old or above ^[1]. It is assumed that the proportion of patients

attaining the target blood glucose level in the present study will be 39%. To ensure the accuracy of the estimate for proportion of patients with $HbA_{1c} < 7\%$, the length of a two-sided 95% confidence interval (CI) should not extend beyond 5%. A sample size of 1463 patients is required to achieve the expected accuracy. Assuming HbA_{1c} measurements are available for 97.5% of the enrolled patients, a total of 1500 patients will be recruited.

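### Protocol 9.2.2 limits recruitment per site by day but sets no total per hospital, so very unequal site sizes could widen the uncertainty of the pooled HbA1c proportion and tilt it towards a few departments

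*Protocol*

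**What the plan says.** Protocol 9.2.1 sets the overall size and the setting: "In this cross-sectional study, approximately 1500 patients will be recruited", and these patients are to be "selected consecutively from departments of endocrinology in at least 30 hospitals of China". Protocol 9.2.2 adds the daily rule: "First 7 consented and suitable patients will be recruited for each site on each day, or fewer if without enough patients".

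Protocol 9.2.2 also lets the sponsor stop a site that misses its expected enrolment. It gives no number, and it concerns shortfall only.

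Protocol 6 plans data collection from 28 Feb to 04 Sep 2017.

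Protocol 9.5 fixes the precision target at a two-sided 95% CI of total length 5 points around an assumed 39%, and concludes: "A sample size of 1463 patients is required to achieve the expected accuracy". It mentions no design effect or intracluster correlation.

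On the analysis side:
- SAP 7.6 tabulates the proportion on FAS – E.
- SAP 7.3, on methods addressing bias, is marked not applicable.
- SAP 7.4 adjusts for identified confounders in a logistic model and does not name hospital.
- SAP 7.9.5 plans disposition summaries but no count per hospital.
- HbA1c is measured in local laboratories (Protocol 9.2.2), and Protocol 9.9 advises caution for that reason.

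**The concern.** The primary result is one pooled proportion from a study whose title calls it nationwide. In an unweighted pooled proportion each hospital counts in proportion to the patients it enrols. A minimum of 30 hospitals therefore spreads the information only if no small group of them supplies most of the patients, and nothing in the readable text secures that. The daily rule limits how fast a site recruits, not how many patients it contributes.

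Two things are at stake. The first is precision: patients at the same hospital tend to resemble one another, and the variance this adds to a pooled proportion grows with the sum of squared site sizes. The second is content: a dominant department would bring its own prescribing habits and its own assay into the estimate, and more patients from the same department would not correct that.

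**Working it through.** **Inputs.** From Protocol 9.5: p = 0.39, total CI length 0.05 (half-width 0.025), 1463 evaluable, 97.5% HbA1c availability. From Protocol 9.2.1 and 9.2.2: about 1500 patients, at least 30 hospitals, 7 per site per day. From Protocol 6: 28 Feb to 04 Sep 2017, which contains 135 weekdays (public holidays not removed). Assumed, because the documents give no value: ICC 0.01, 0.03 and 0.05, and every split of patients between hospitals.

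**Step 1: reproduce the plan's figure.** n = 1.96² × 0.39 × 0.61 / 0.025² = 1462.2, so 1463. Enrolment: 1463 / 0.975 = 1500.5, in line with the planned 1500. The CI length at 1463 is 2 × 1.96 × √(0.39 × 0.61 / 1463) = 5.00 points. The plan's arithmetic is sound if patients are independent.

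**Step 2: what the daily limit allows.** 7 × 135 = 945, and 945 / 1500 = 63%. With 30 hospitals the average is 1500 / 30 = 50 each, and 50 / 7 = 7.1, so a site passes the average on its eighth full day. The daily rule hardly restricts the total.

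**Step 3: effect of site sizes.** For an unweighted pooled proportion, Kish's design effect is

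DEFF = 1 + (Σm² / Σm − 1) × ICC, and CI length = 5.00 × √DEFF.

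- *Equal sites:* m = 1463 / 30 = 48.8, so Σm²/Σm = 48.8.
- *Three hospitals supply half:* three of 243.8 and 27 of 27.1, so Σm²/Σm = 0.5 × 243.8 + 0.5 × 27.1 = 135.5.
- *Cap of 75, very unbalanced:* 19 × 75 = 1425, and 11 hospitals share the other 38 (3.45 each), so Σm²/Σm = (1425 × 75 + 38 × 3.45) / 1463 = 73.1.

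| Split of 1463 over 30 hospitals | DEFF at ICC 0.01 / 0.03 / 0.05 | CI length, points |
|---|---|---|
| Equal | 1.48 / 2.43 / 3.39 | 6.1 / 7.8 / 9.2 |
| Three supply half (hypothetical) | 2.34 / 5.03 / 7.72 | 7.7 / 11.2 / 13.9 |
| Cap 75, very unbalanced | 1.72 / 3.16 / 4.61 | 6.6 / 8.9 / 10.7 |

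Under a cap of 75, Σm²/Σm cannot exceed 75. The strict bound is therefore DEFF = 1 + 74 × ICC = 1.74 / 3.22 / 4.70, or 6.6 / 9.0 / 10.8 points. The last row of the table is within 0.1 point of it.

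**Step 4: separate the two parts.** At ICC 0.03, clustering with equal sites multiplies the variance by 2.43. Having three hospitals supply half multiplies it by a further 5.03 / 2.43 = 2.07. Under the cap that further factor is 3.16 / 2.43 = 1.30. A cap acts only on this second factor.

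**The case against.** The strongest reply is that severe imbalance is unlikely. Every site, however busy, is held to 7 a day. Thirty sites recruiting at that rate enrol 210 a day and would finish in 1500 / 210 = 7.1, about 8 days, with some 50 each. For one site to supply 945 it would have to recruit fully on every weekday of the window while the other 29 averaged (1500 − 945) / 29 = 19. This stands: 945 is a ceiling, and the three-hospital split is an illustration. A reader might infer that enrolment is competitive, or that a few hospitals will dominate. The documents say neither, and the sponsor's right to stop a site for missing its enrolment goal suggests that site goals exist. Those goals are not maxima, however, and closing slow sites would concentrate the sample further.

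A second reply is that larger departments contributing more patients is not in itself bias if the target is patients, and that a cap does not make hospitals a probability sample of China. That also stands. The case for a cap is mainly one of precision and of limiting dependence on a few local laboratories.

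A third is that clustering itself is the larger issue. At ICC 0.03 equal sites already give 7.8 points against 5. This is correct, and it is why a cap is not enough alone.

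Finally, the study figures, some SAP sections and the site contracts cannot be seen, and a number per site could be there.

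**Conclusion.** The point holds as a cheap improvement to the design, not as an error in the plan. The readable text gives no maximum per hospital, and nothing in the planned analysis offsets unequal site sizes. If three hospitals supplied half of the evaluable patients, the CI would be longer than with equal sites by 1.6, 3.4 and 4.7 points at ICC 0.01, 0.03 and 0.05. A cap of 75 would hold that excess to about 0.5, 1.1 and 1.5 points in a near-worst split.

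These sizes rest on an assumed ICC, an assumed split, exactly 30 hospitals and 1463 evaluable patients. The direction holds for any ICC above zero. A reader might also infer that a cap would bring back the 5-point length. It would not, since even equal sites miss it at every ICC considered.

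**What to change.** 1. Add a total cap per hospital to Protocol 9.2.2, enforced in the EDC system. A value of 75 is illustrative: it is 5% of 1500 and 1.5 times the average of 50. Thirty hospitals at 75 allow 2250, so 1500 stays reachable, and at 7 a day a site needs about 11 of the 135 weekdays to fill it. If a limit already exists in site contracts, state it in the protocol.
2. Tabulate enrolled and evaluable patients per hospital with the disposition summaries in SAP 7.9.5.
3. In SAP 7.6, report the primary proportion with a 95% CI adjusted for clustering by hospital.

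The cost is one protocol sentence, one system limit, one table and one change of variance estimator. The real downside is that fast sites can no longer make up fully for slow ones.

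Timing matters. Planned data collection ended on 04 Sep 2017 and the SAP is dated 09 Feb 2018, before database lock. If enrolment has closed, item 1 is no longer available, but items 2 and 3 still are and would show how unequal the sites turned out to be.
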